IcEv1 (Death not due to COVID-19)	Hypothetical strategy
IcEv2 (Non-study COVID-19 vaccine)	Hypothetical strategy
IcEv3 (Early infection)	Principal stratum strategy
IcEv4 (Study infection)	Composite strategy
IcEv5 (Confounding On-study Medications)	Hypothetical strategy
Rationale for Strategies	Early infection (IcEv3) results in complete exclusion from analyses because prior to Day 36, the vaccine may not have achieved full efficacy. Additional exploratory analyses are performed where participants with early infection occurring after Day 1 but before Day 36 are included.

Table 17 Estimands for Primary Safety Analyses for Phase 1/2/3a, Phase 3b, Phase 3c and Pooled Cohorts

Estimand Label	Estimand 3 (Safety – Unsolicited AEs/AEs leading to discontinuation or withdrawal/MAAE/SAE)
Estimand Description	Count and percentage of vaccinated participants who would develop unsolicited AEs, AEs leading to discontinuation/withdrawal, MAAEs, and SAEs. These will be evaluated with each dose of study vaccine, ARCT-154 or placebo.
Target Population	The population who are enrolled in the study and receive any dose of study vaccine (Phase 1, 2, 3a, 3b, 3c-1, and 3c-2 participants)
Endpoint	Occurrence of unsolicited AEs will be analyzed up to 28 days after each study vaccine administration. Occurrence of AEs leading to discontinuation/withdrawal, MAAEs, or SAEs will be analyzed up to Day of Switchover/Further Study Vaccine, receipt of non-study vaccine, early withdrawal, or last on-study assessment visit, whichever comes first. Occurrence of AEs leading to discontinuation/withdrawal, MAAEs and SAEs after the Switchover/Further Study Vaccine will be recorded and summarized for the interval from the switchover/Further Study Vaccine up to Day 394 (Phase 1/2/3a and Phase 3b only). For Phase 1/2/3a and 3b, AEs in participants who do not undergo Switchover/Further Study Vaccine will be recorded for the interval from Day 92 up to Day 394
Treatment Conditions	Phase 1/2/3a and 3b: ARCT-154 dose 5 µg or placebo administered on Day 1, Day 29, or at Switchover/Further Study Vaccine (Day 92 and Day 120) Phase 3c: ARCT-154 dose 5 µg or ChAdOx1 administered on Day 1 and Day 29.
Population-Level Summary	Percentage of vaccinated participants who develop each type of AE
Intercurrent Event (IcEv) Strategy	
IcEv1 (Death not due to COVID-19)	Composite strategy
IcEv2 (Non-study vaccine)	Treatment policy strategy
IcEv3 (Early infection)	Composite strategy

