Estimand 3	Percentage of vaccinated participants who would develop unsolicited AEs, AEs leading to discontinuation/withdrawal, MAAEs, and SAEs within timeframe up to the earlier of Day 92/Switchover/Further Study Vaccine or receipt of non-study COVID-19 vaccine. A treatment policy strategy is used for assessing safety irrespective of a current (or prior) SARS-CoV-2 infection at time of the study vaccination. See Table 17 for full definition. Events occurring before and after Switchover/Further Study Vaccine will be analyzed separately.	Phase 1/2/3a SAS Phase 2/3a SAS Phase 3b SAS Phase 3c SAS Pooled SAS	SARS-CoV-2 infections and death due to COVID-19 (if they meet the AE and time window criteria) are included in the endpoint (composite strategy).	Summaries of number of participants (%) with unsolicited AEs (including summary by severity and relatedness to study vaccine), AEs leading to discontinuation/withdrawal, MAAEs, and SAEs will be presented. The Clopper-Pearson 95% CIs will be presented for the incidence rate of these events. See Section 8.7.3.2 and the SAP for further details.	Sensitivity analyses will also be performed in the Phase 1/2/3a ITT Phase 2/3a ITT Phase 3b ITT Phase 3c ITT Pooled ITT Supportive: Analysis will be performed for different time intervals, specifically: All MAAEs, AE/SAEs, AEs leading to discontinuation/withdrawal up to Day 29, Day 57, Day 92, and Day 394 or Final Visit/Early Termination Visit/receipt of non-study COVID-19 vaccine after the first vaccination will be summarized accordingly. AEs occurring after the Day 92 will be recorded and summarized for the interval Day 92 up to Day 394 (Phase 1/2/3a and Phase 3b only). For Phase 1/2/3a and 3b, AEs in participants that do not receive additional study vaccine at Day 92 will be recorded separately for the interval
------------	--	---	---	---	---

Table 18 Summary of Statistical Methods, Including Sensitivity Analyses

Estimand Label	Estimand Description	Main Estimation			Sensitivity Analysis
		Analysis Set	Imputation/Data/Censoring Rules	Analysis Model/Method	
					from Day 92 up to Day 394 All AEs including those occurring after receipt of a non-study COVID-19 vaccination will be summarized separately as supportive analyses, if applicable.

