#### 6.6.1.2 Unsolicited Adverse Events

Unsolicited AEs are defined as any spontaneously reported or discovered AE. Unsolicited AEs can also be solicited AE that leads to: A medically attended visit, an SAE, a discontinuation of study vaccine, a withdrawal from the study, or any solicited AE that persists beyond 7 days after the first study vaccine administration.

Unsolicited AEs will be coded using the MedDRA and displayed in tables using System/Organ/Class (SOC) and Preferred Term (PT). Treatment emergent AEs will be presented in tables, and all AEs will be included in listings where applicable.

In any tabulation, unsolicited AEs will be summarized by participant, therefore, a participant contributes only once to the count for a given Unsolicited AE (SOC or PT) in the tabulation. All episodes of all events will be provided in listings.

Unsolicited AEs with onset during the first 28 days after vaccination will be analyzed in the following analysis sets as defined below:

Analysis set	Timepoint
Phase 1/2/3a SAS	

After Dose 1, after Dose 2, after Dose 1 or 2

After Dose 3, after Dose 4

After Any dose

Phase 3b SAS	

After Dose 1, after Dose 2, after Dose 1 or 2

After Dose 3, after Dose 4

After Any dose

Phase 3c SAS	

After Dose 1, after Dose 2, after Dose 1 or 2

	• After Any dose
Pooled SAS	• After Dose 1, after Dose 2, after Dose 1 or 2
	• After Dose 3, after Dose 4
	• After Any dose

Participants will be considered for the computation of percentages in the specified time interval if they received the study vaccine in the specified interval. For each time interval the number of participants without missing dose will be presented.

Only data up to receipt of non-study COVID-19 vaccine (IcEv2) will be included in summary tables. Participant's data after the receipt of non-study COVID-19 vaccine will be summarized separately in a similar manner as unsolicited AEs for the following time interval: from the receipt of non-study COVID-19 vaccine up to the Final Visit/ET.

The following summaries will be presented for unsolicited AEs:

- Overview of number and percentage of participants with at least one:
  - AE
  - Related AE
  - AE by severity
  - MAAE
  - Related MAAE
  - SAE
  - Related SAE
  - AE leading to premature discontinuation of vaccine series

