Section 8.3.1 Table 17 (estimand 3) Unsolicited Adverse Events	In the protocol, it was specified that events occurring after non-study vaccine administration or early COVID-19 infection could contribute spurious safety data, so only the events occurring prior the non-study vaccine administration or early	Events occurring after non-study vaccine administration or early COVID-19 infection could contribute spurious safety data, so only the events occurring prior the non-	Reverting back to protocol definition.

Protocol Section	Analysis method described originally in the protocol	Planned Analysis	Reasons of changes
	
COVID-19 infection will be included in the analysis. Events occurring after these will be summarized separately.
 
In SAP part 2 section 8.1.2, it was specified that no censoring of events after receipt of non-study COVID-19 vaccine would be performed. All events would be presented, irrespective of whether non-study vaccine was received. The rationale provided for the change was the following:
 
Randomization should ensure no imbalance in the number of participants receiving non-study COVID-19 vaccine.
	study vaccine administration or early COVID-19 infection will be included in the analysis.	
Section 8.2 Safety Analysis Set (SAS)	
Includes all participants who receive any dose of study vaccine (ARCT-154 or placebo). Participants will be analyzed according to the study vaccine received.
	
In SAP Part 1/2, the definition was modified to “Includes all participants who receive any dose of study vaccine (ARCT-154 or placebo). Participants with no safety data after receipt of study vaccine will not be included in the SAS. Participants will be analyzed according to the study vaccine received.”
 
This change is not implemented in the final SAP.
	Reverting back to protocol definition.

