### 9.2.3 Estimands for Primary Safety Analyses for Phase 1/2/3a, Phase 3b, Phase 3c and Pooled Cohorts

Estimand Label	Estimand 3 (Safety – Unsolicited AEs/AEs leading to discontinuation or withdrawal/MAAE/SAE)
Estimand Description	
Count and percentage of vaccinated participants who would develop unsolicited AEs, AEs leading to discontinuation/withdrawal, MAAEs, and SAEs.
 
These will be evaluated with each dose of study vaccine, ARCT-154 or placebo.

Target Population	The population who are enrolled in the study and receive any dose of study vaccine

Endpoint	Occurrence of unsolicited AEs will be analyzed up to 28 days after each study vaccine administration.  Occurrence of AEs leading to discontinuation/withdrawal, MAAEs, or SAEs will be analyzed up to Day of Switchover/Further Study Vaccine, receipt of non-study vaccine, early withdrawal, or last on-study assessment visit, whichever comes first.  Occurrence of AEs leading to discontinuation/withdrawal, MAAEs and SAEs after the Switchover/Further Study Vaccine will be recorded and summarized for the interval from the switchover/Further Study Vaccine up to Day 394 (Phase 1/2/3a and Phase 3b only).  For Phase 1/2/3a and 3b, AEs in participants who do not undergo Switchover/Further Study Vaccine will be recorded for the interval from Day 92 up to Day 394
Treatment Conditions	Phase 1/2/3a and 3b: ARCT-154 dose 5 µg or placebo administered on Day 1, Day 29, or at Switchover/Further Study Vaccine (Day 92 and Day 120)  Phase 3c: ARCT-154 dose 5 µg or ChAdOx1 administered on Day 1 and Day 29.
Population-Level Summary	Percentage of vaccinated participants who develop each type of AE
Intercurrent Event (IcEv) Strategy	
IcEv1 (Death not due to COVID-19)	Composite strategy
IcEv2 (Non-study vaccine)	While on treatment strategy
IcEv3 (Early infection)	Composite strategy

IcEv4 (Study infection)	Composite strategy
IcEv5 (Confounding On-study Medications)	treatment policy strategy
Rationale for Strategies	Events occurring after IcEv2 could contribute spurious safety data so a while on treatment policy is used for these events and events occurring after this IcEv's will be summarized separately.
Estimand Label	Estimand 4 (Reactogenicity – Solicited AEs)
Estimand Description	Count and percentage of vaccinated participants who would develop solicited AEs. These will be evaluated after vaccination on Day 1 and Day 29, ARCT-154 or placebo.

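### SAP 7.3 cuts off unsolicited AEs at early COVID-19 infection and calls this the protocol rule, but the protocol and the rest of the SAP cut off only at non-study vaccine

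*SAP*

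**What the plan says.** The row for Table 17, estimand 3 (Unsolicited Adverse Events) in SAP 7.3 has three parts that matter.

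- Its account of the protocol: "events occurring after non-study vaccine administration or early COVID-19 infection could contribute spurious safety data", so that only events before either of them count. It adds that events after them are reported apart: "COVID-19 infection will be included in the analysis. Events occurring after these will be summarized separately".
- Its Planned Analysis column repeats the restriction, ending "study vaccine administration or early COVID-19 infection will be included in the analysis". This cell does not mention a separate summary.
- Its reason: "Reverting back to protocol definition".

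Other places state a different rule for the same estimand.

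- Protocol 8.3.1, Table 17, estimand 3: "IcEv3 (Early infection) Composite strategy". The rationale sets apart only events after non-study vaccine.
- Protocol 8.7.2, Table 18, estimand 3: "SARS-CoV-2 infections and death due to COVID-19 (if they meet the AE and time window criteria) are included in the endpoint (composite strategy". The description adds that safety is assessed whatever the infection status at vaccination.
- SAP 9.2.3, estimand 3: early infection is composite, and the rationale names one event only: "Events occurring after IcEv2 could contribute spurious safety data so a while on treatment policy is used".
- SAP 6.6.1.2: "Only data up to receipt of non-study COVID-19 vaccine (IcEv2) will be included in summary tables". A separate summary is planned only for data after non-study vaccine.

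**The concern.** SAP 7.3 is not an amendment log of superseded text. Its Planned Analysis column states what this SAP will do, and SAP 9.2 sends the reader to Section 7 for updates to the estimands. A programmer could therefore take 7.3 as controlling and truncate at early infection. The stated reason is correct for the non-study-vaccine half of the rule, which makes the other half easy to miss.

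The estimand concerned is a primary safety estimand. Vaccine-associated enhanced respiratory disease is a named risk in Protocol Table 1 and can appear only after infection. Truncating at early infection would take any such event in that window out of the unsolicited AE tables, together with the same participants' later AEs of every other kind. SAP 6.6.1.3 summarizes SAEs, MAAEs and AEs leading to discontinuation in the same manner as unsolicited AEs, so the truncation could extend to those tables.

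**Working it through.** No figure in the plan is at issue. The check is a comparison of the estimand 3 rules, followed by the direction of the effect if 7.3 were applied.

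**Step 1. The rules side by side**

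| Place | After non-study vaccine (IcEv2) | After early infection (IcEv3) |
|---|---|---|
| Protocol Table 17 | set apart, summarized separately | composite, counted |
| Protocol Table 18 | censored from the main interval | infections and COVID-19 deaths counted |
| SAP 6.6.1.2 | removed, summarized separately | no truncation |
| SAP 7.1 | renamed while on treatment | not changed |
| SAP 9.2.3 | while on treatment | composite, counted |
| SAP 7.3 | removed | removed |

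SAP 7.3 stands alone in the last column. The only Table 17 rationale in the protocol that treats early infection as a source of spurious data belongs to estimand 4, the solicited events.

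**Step 2. Which events the 7.3 rule would reach**

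SAP Table 5 defines early infection as a positive test or anti-nucleocapsid seropositivity before vaccination, or infection up to 7 days after dose 2 (Day 35). Infection from Day 36 is IcEv4, which 7.3 does not touch and 9.2.3 keeps composite.

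- *Infected after dose 1.* Protocol 5.2.1 allows dose 2 later, at least 28 days after the positive RT-PCR result. Every unsolicited AE after that person's dose 2 would follow the infection and be removed.
- *Seropositive at baseline.* Protocol 5.1.2 does not exclude a positive nucleocapsid test. If early infection in 7.3 is read as IcEv3, such a participant has no time before the event, and every AE would be removed.

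**Step 3. Effect on the percentages**

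Under SAP 6.6.1.2 the denominator is everyone vaccinated in the interval, with no removal for early infection. If a share f of participants had all their AEs removed, and their AE risk were otherwise the same as everyone else's, then

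apparent rate = true rate × (1 − f).

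The documents give no value for f. For assumed values and a true rate of 1.0%:

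- f = 2%: 1.0% × 0.98 = 0.98%
- f = 5%: 1.0% × 0.95 = 0.95%
- f = 10%: 1.0% × 0.90 = 0.90%
- f = 20%: 1.0% × 0.80 = 0.80%

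These values show the direction and how the effect scales. They are not an estimate for this trial.

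**Step 4. How much of the infection window is early**

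If the infection hazard were constant over Day 1 to Day 92 (an assumption), 35/92 = 38% of on-study infections would be early. The other 57/92 = 62% would fall under IcEv4, and the events after them would stay in the tables.

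**The case against.** The strongest reply is that the operative text already includes these events. Section 7.3 lists changes from the two earlier SAPs that are not carried forward. The change reversed in this row concerns non-study vaccine: SAP Part 2 would not have censored after it. For that, a return to the protocol is an accurate description. The methods text (6.6.1.2), the estimand table (9.2.3) and the list of estimand corrections (7.1) agree with one another. The early-infection phrase also appears in the estimand 4 row of SAP 7.2, where the protocol does name that event, so it may simply have been carried over. This is a good argument that the phrase is a drafting error. It does not remove the error, because 7.3 states a rule in the current plan and 9.2 points to Section 7.

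The row's account of the protocol also mentions a separate summary, so the events might be moved and not lost. The Planned Analysis cell omits that sentence, however, and 6.6.1.2 provides a separate summary only after non-study vaccine. SAP 7.2 also drops the ITT sensitivity analysis of unsolicited AEs.

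A reader might go further and infer that the plan hides the events in which enhanced disease would show. The documents do not support that.

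- Events after infection from Day 36 stay in the safety tables.
- Adjudicated severe COVID-19 and COVID-19 deaths at any time after dose 1 are analysed as Exploratory 1 and 2 in SAP Table 6, for participants without prior infection.
- SAP 6.4 tabulates adjudicated cases by Day 1–35 and Day 36–92 in the randomized and ITT sets, which do not exclude baseline seropositives. It also presents severe cases and deaths.
- SAEs and fatal AEs are listed for the randomized set (SAP 6.6.1.3), and the DSMB reviews severe cases for enhanced disease (Protocol 8.10.3).

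What those sources do not replace is the tabulation of AEs other than COVID-19 in the affected participants.

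A reader might also infer an imbalance between arms. Early infection could differ by arm once the vaccine begins to act, but no document shows that it does.

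**Conclusion.** The contradiction stands. SAP 7.3 adds early infection as a cut-off for estimand 3 and attributes it to the protocol. Protocol Tables 17 and 18 and SAP 9.2.3 count events after early infection, and SAP 6.6.1.2 and 7.1 remove events only after non-study vaccine.

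The consequence is conditional and bounded. It arises only if 7.3 is programmed instead of 6.6.1.2, and it reaches only events that follow infection before vaccination or up to Day 35. Within that scope AE incidence would be understated, because the numerator shrinks and the denominator does not. The size cannot be given, since the documents report no number of early infections or baseline seropositives. Complete loss of AEs in baseline seropositives rests on reading the phrase in 7.3 as IcEv3, which the row does not say.

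Confidence is high for the wording conflict and low for any particular size of effect. It should be corrected because it concerns a primary safety endpoint and the correction costs little.

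**What to change.** In the estimand 3 row of SAP 7.3:

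1. Delete *or early COVID-19 infection* from both the column describing the protocol and the Planned Analysis column.
2. Correct the account of the protocol, so that the return to its definition refers to non-study vaccine only.
3. State that IcEv3 and IcEv4 stay composite as in 9.2.3, with truncation only at IcEv2 as in 6.6.1.2, and that this also holds for SAEs, MAAEs and AEs leading to discontinuation.

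The cost is a few words of SAP text. Programs already written to 6.6.1.2 need no change. A companion overview without COVID-19 preferred terms would be a reasonable extra but is optional and not part of this correction.

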## 8 REFERENCES

Please see the protocol Section 13 for relevant study references.

## 9 APPENDICES

### 9.1 Schedule of Assessments

Protocol Appendix 1 contains the study's schedule of assessments.

## 9.2 Estimands

The following sections provide full description of the protocol estimands. Updates made to these are described in section 7 .

### 9.2.1 Estimands for Phase 1/2/3a Substudy and Phase 3c Substudy Primary, Secondary and Exploratory Immunogenicity Endpoints

Estimand Label	Estimand 1 (immunogenicity)
Estimand Description	NAb by surrogate virus neutralization test (primary) and NAb by PRNT50 and BAb (secondary) responses at defined time points following vaccination (as defined in Section 1.2) with ARCT-154 or placebo. The primary endpoint will be measured based on responses at Day 57.
Target Population	Vaccinated participants (as defined by eligibility criteria) in Phases 1, 2 and 3a. The population includes participants without evidence of COVID-19, SARS-CoV-2 infection, or nucleocapsid antibody positivity on or prior to Day 57.
Endpoint	NAb and BAb responses as defined in Section 1.2
Treatment conditions	ARCT-154 dose 5 µg or placebo administered on Day 1 and Day 29.
Population-level Summary	

Geometric mean concentrations for NAb and BAb

The geometric mean ratio (ARCT-154 /Placebo) for NAb and BAb concentrations

Proportion of participants in each study vaccine group that demonstrate seroconversion (as defined by 4-fold increase in antibody concentration [based on international units, if available] from baseline).

Geometric mean fold rise (GMFR) for NAb and BAb

Intercurrent events (IcEv) Strategy	
IcEv1 (Death)	Treatment policy strategy
IcEv2 (Non-Study vaccine)	While on treatment strategy
IcEv3 (Early infection)	Principal stratum strategy
IcEv4 (Study infection)	Principal stratum strategy
IcEv5 (confounding on-Study Medications)	While on treatment strategy
Rationale for strategies	IcEv2 and IcEv5 could be potentially confounding to the analysis of the endpoint and result in censoring of the participant for all endpoint assessments after the time of the IcEv (while on treatment). IcEv4 and IcEv3 could also be potentially confounding but it is more difficult to determine the

	precise timing of these events, so a principal stratum strategy is used to exclude these participants from immunogenicity analyses.
--	---

### 9.2.2 Estimands for Phase 1/2/3a, Phase 3b, and Pooled Primary, Secondary and Exploratory Efficacy Analyses

Estimand Label	Protocol Estimand 2 (Vaccine Efficacy)
Estimand Description	
 
VE estimated as 1-HR, where HR is the hazard ratio from the adjusted Cox Proportional Hazard model for virologically confirmed COVID-19 detected after 7 days post the second study vaccine dose.
 
VE estimated as 1-HR, where HR is the hazard ratio from the adjusted Cox Proportional Hazard model for virologically confirmed COVID-19 detected at any time after first vaccine dose
 

Target Population	Eligible participants who have received both doses of study vaccine in the initial series. The population includes participants without evidence of COVID-19, SARS-CoV-2 infection, or nucleocapsid antibody positivity on or prior to Day 35.
Endpoint	
VE for COVID-19/severe COVID 19/death due to COVID-19 (dependent on the endpoint concerned) detected after 7 days post the second study vaccine dose and based upon virologically confirmed COVID-19, estimated as 1-HR, where HR is the hazard ratio from the adjusted Cox Proportional Hazard model
 
Additional endpoints will include VE for virologically confirmed COVID-19 detected at any time after first vaccine dose estimated as 1-HR, where HR is the hazard ratio from the adjusted Cox Proportional Hazard model.

Treatment Conditions	ARCT-154 dose 5 µg or placebo administered on Day 1 and Day 29.
Population-Level Summary	See 'Endpoint' above
Intercurrent Event (IcEv) Strategy	

 
• IcEv1 (Death not due to COVID-19)
 
	Treatment policy strategy

 
• IcEv2 (Non-study COVID-19 vaccine)
 
	Treatment policy strategy

 
• IcEv3 (Early infection)
 
	
Principal stratum strategy for analyses where events only counted from 7 days after second vaccination
 
Composite strategy where events counted at any time after first vaccination

 
• IcEv4 (Study infection)
 
	Composite strategy

 
• IcEv5 (Confounding On-study Medications)
 
	Treatment policy strategy
Rationale for Strategies	Early infection (IcEv3) results in complete exclusion from analyses from the primary endpoint because prior to Day 36, the vaccine may not have achieved full efficacy. Additional secondary and exploratory analyses are performed where participants with early infection occurring after Day 1 but before Day 36 are included.

